## 3. STUDY DESIGN

Observational study with specimen collection.

#### 4. STUDY SETTING

The study, which will characterise tumour proteomes and tumour-specific neoantigens, will benefit from work contributed by NHS hospitals and NHS cancer centres across the UK. Up to 15 sites will be involved in recruiting participants and collecting samples. Tumour specimens will be transported to the School of Life Sciences, University of Dundee, for neoantigen analysis by Platinum informatics Ltd. utilising laboratory facilities at the University of Dundee.

#### 5. PARTICIPANT ELIGIBILITY CRITERIA

#### 5.1. Inclusion criteria

- 18 years of age or older
- Willing and able to provide written informed consent
- Histologically confirmed oesophageal or gastroesophageal junctional adenocarcinoma.
- Able to provide a tumour biopsy sample as per protocol requirements (see section 6.4)

## 5.2. Exclusion criteria

- Concurrent systemic anti-cancer treatment and/or radiotherapy (participants undergoing cancer surgery are eligible.)
- Any significant medical condition that in the opinion of the Principal Investigator (PI) would impair the ability of the participant to complete the requirements of the protocol

## 6. STUDY PROCEDURES

#### 6.1. Recruitment

75 participants across all sites will be recruited. Where it was not possible to obtain a tumour biopsy further participants will be recruited to ensure tumour biopsies are obtained from up to 75 participants (approximately 50 oesophageal samples/25 lower oesophageal-gastric samples).

#### 6.1.1. Participant identification

Patients will be identified during routine clinical care pathways by the existing clinical care team. Patients may be identified as part of case reviews at upper gastrointestinal cancer multidisciplinary team meetings and during other routine clinical care contacts. Subsequently, patients will be reviewed as part of their routine care by the PI or a sub-investigator, also part of the patient's clinical care team, who will confirm if the patient meets the study inclusion criteria and will then make the initial approach to discuss the study with them.

Suitable patients will be first approached at clinic by the PI or sub-investigator who is part of their clinical care team. They will be provided with information about the study (Participant Information Sheet) and the consent form. They will have the opportunity to ask questions, to think about their involvement, to talk to others about the study and if willing to take part, will return to give consent at a later date. Participants will be given a minimum of 24 hours from initial approach and discussion to consider whether they wish to take part in the study. The time given to consider taking part is unlimited as long as standard of care treatment is not started. The start of their standard care treatment will not be delayed.

#### 6.1.2. Screening

Screening will be performed by local sites under the overall responsibility of the local PI who will be required to confirm that the participant satisfies all the approved inclusion and exclusion criteria of the protocol. No post-consent screening will be conducted.

#### 6.1.3. Ineligible participants

After a patient has been approached about the study if they are found to be ineligible for study participation, they will be thanked and the reasons for the ineligibility fully explained. Any queries or questions will be answered by an appropriate member of the research team.

#### 6.1.4. Payment

No payment for participation in the study will be made. Where any research visits are not conducted at the time of a clinical visit, travel expenses will be given.

### 6.2. Consent

The PI retains overall responsibility for the conduct of research at their site and this includes taking of informed consent at each site. They must ensure that any person delegated responsibility for seeking informed consent is duly authorised, trained, and competent according to the approved protocol and principles of GCP.

Participants will receive a copy of the Participant Information Sheet (PIS) and will be given at least 24 hours to consider participation in the study prior to consent. Prior to consent participants will be given the opportunity to ask any questions about the study. Where a participant requests to speak with a physician from the study team the consent process will not be completed until the participant has spoken to the physician and had all questions answered to their satisfaction. Once a patient agrees to participate, written informed consent will be obtained and eligibility confirmed.

At time of consent participants will be asked if they only consent to give tissue samples when this is feasible during standard clinical procedures or, where this is not possible, if they give consent to have a biopsy solely for the purpose of obtaining research samples.

Participants may provide additional consent for further biopsies to be taken during further routine clinical care procedures as an optional part of the study.

Written informed consent will be obtained from participants for blood and tissue collection as well as for genomic analysis of these specimens.

The original Informed Consent Form (ICF) will be filed in the TMF or Investigator Site File (ISF), a copy will be given to the participant and a further copy will be filed in the participant's medical notes.

For adults who lose capacity their previous wishes will remain valid unless the protocol changes significantly. If this occurs and further consent is required from a participant who has lost capacity, an appropriate person will be asked for their consent. This will be fully documented in the patient's notes. Data or tissue already collected with consent will be retained and used in the study.

## 6.2.1. Additional consent provisions for collection and use of participant data and biological specimens in ancillary studies, if applicable

Consent for retention of surplus biospecimen material remaining after the completion of PROTEAN study analysis for future ethically approved research into the causes of or treatments for oesophageal/gastroesophageal adenocarcinoma will be requested. Surplus material will be stored in the Tayside Biorepository (TBR) and registered with Tayside Biorepository (REC approval17/ES/0130) to ensure traceability and to provide support required for any services involving the tissue. TBR is part of the Scottish Biorepository network which operates as a unified network and is accredited by NHS Research Scotland Central Management Team to

ensure that best practice for human tissue research within Scotland is carried out to the equivalent standards of the Human Tissue Authority. Request to access samples for further research will be made by the CI and Trial Scientific Adviser (TSA) or will be made in writing by other investigators using a standardised format, to the CI and TSA who will review the request. An application will be submitted to the TBR detailing the requirement for further use. This will undergo scientific and ethical review by the biorepository tissue access committee who will confirm suitable tissue and samples are available. The access committee will ensure that use of the tissue is compliant with the consent provided by patients and the REC delegated ethical authorisation to TBR (17/ES/0130).

### 6.3. Baseline data

Baseline data will be collected as per Schedule of Procedures, Appendix 4. Only information directly related to the objectives and outcome measures detailed in the protocol shall be collected.

#### 6.4. Study assessments

Study assessments will be carried out as per Schedule of Procedures, see Appendix 4

Medical history

- To confirm eligibility
- Location of primary tumour
- Histological and molecular diagnosis details Human epidermal growth factor receptor 2 (HER2), PD-L1 testing
- Tumour stage according to AJCC/UICC version 8 for cancers of the oesophagus and stomach
- Stage and location of metastases
- Progression assessment RECIST Criteria 1.1
- Medical co-morbidities
- Smoking history

Demographics

• Age, gender, body mass index

#### Concomitant medication

• Details of any scheduled or prior cancer treatment

#### Biopsy

- A fresh tumour biopsy will be collected:
  - Prior to the commencement of any subsequent scheduled anticancer treatments\*;
     OR
  - After the completion of the latest line of anticancer treatment\*; OR
  - During follow up when a participant is not receiving or is between scheduled anticancer treatments\*.

\*Anti-cancer treatments excluding surgery

- The biopsy may be obtained from any site of tumour, primary or metastatic as considered the most appropriate and feasible at the time of the procedure.
- Biopsies from more than one tumour site may be obtained at the same time point and procedure, but this is not mandatory, only biopsy of a single tumour site is required for study participation.
- Up to 10 biopsies, approximately 2mm each, will be taken at each timepoint and if tumour biopsy is being undertaken by endoscopy 2 biopsies approximately 2mm each of adjacent normal oesophageal or gastric mucosa.
- As far as possible, tumour biopsies for the study will be obtained during routine clinical care procedures e.g. endoscopy, surgery, stenting. However, where this is not possible, consent will be requested for study specific procedures for biopsy to obtain tumour material.
- Participants may provide additional consent for further biopsies during further routine clinical care procedures to be taken as an optional part of the study.
- Details of sample collection, processing, storage and transfer will be provided in PROTEAN Clinical Sample Handling Manual.

### Research bloods

- A maximum of 20ml of blood will be collected at each visit.
- Sites which have the facilities to carry out peripheral blood mononuclear cell preparations (PBMC) analysis will process and complete analysis on site. These samples will be processed at sites for PBMCs.
- Details of sample collection, processing, storage and transfer will be provided in PROTEAN Clinical Sample Handling Manual.

#### Outcome assessment

- Tumour response status according to RECIST v1.1
- Overall Survival

Adverse events (AE)

• Will be recorded as per Section 8, Pharmacovigilance.

## 6.5. Long term follow-up assessments

Nil

## 6.6. Qualitative assessments

Nil

## 6.7. Withdrawal criteria

Participants are free to withdraw at any time and are not obliged to give reason(s). It will be clearly stated in the PIS that the participant is free to withdraw from the study at any time for any reason without prejudice to future care. The CI, PI or delegate will make a reasonable effort to ascertain the reason(s), both for those who express their right to withdraw and for those lost to

follow up, while fully respecting the individual's rights. Following a request to withdraw from the study this will be acted on immediately by the local study team and communicated to the CI.

The investigator may withdraw a participant at any time if it is in the best interest of the participant and continuation would be detrimental to the participant's well-being. A full explanation will be provided.

If a participant withdraws or is withdrawn from the study, the research team will retain any data and samples obtained up until the time of the point of withdrawal for use in the study analysis. Participants do not have the right to withdraw their data or any research tissue collected. No further data or samples will be collected after withdrawal.

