## 8.2. Operational definitions for (S)AEs

As this study involves the collection of blood and tissue samples with no intervention, AEs will only be recorded where, in the opinion of the CI/PI, they are directly associated with the collection of these samples. AEs occurring during the collection of samples, where this is being done at the same time as a standard care procedure, will only be recorded if, in the opinion of the CI/PI, this is directly associated with the additional sampling required for the study.

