#### 8.3. Recording and reporting of AEs/SAEs

All AEs will be recorded on the AE Log in the electronic case report form (eCRF) and will be assessed for severity by the CI or PI. AEs will be recorded from the time a participant consents to join the study until the participant's last study visit. An AE may be classified as a SAE.

AEs/SAEs will be followed up until recovered/recovered with sequelae/death/30 days after participant's last visit - whichever is the soonest.

**SAEs which are both unexpected and related to study participation** will be submitted on an HRA non-CTIMP Safety Report form to the REC by the CI, within 15 days of becoming aware of the SAE, and copied to the Sponsor Research Governance Office.

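### Sections 6.7 and 8.3 contradict each other on a sampling-related adverse event still unresolved at withdrawal, so its outcome may go unrecorded

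*Protocol*

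**What the plan says.** Protocol section 6.7 covers two routes out of the study: the participant's own decision, and withdrawal by the investigator ("The investigator may withdraw a participant at any time if it is in the best interest of the participant and continuation would be detrimental" to well-being). For both routes, "the research team will retain any data and samples obtained up until the time of the point of withdrawal", and then: "No further data or samples will be collected after withdrawal". No exception is written for safety data.

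Section 8.3 sets two periods. For recording: "AEs will be recorded from the time a participant consents to join the study until the participant's last study visit". For follow-up: "AEs/SAEs will be followed up until recovered/recovered with sequelae/death/30 days after participant's last visit - whichever is the soonest". Withdrawal is not among the end points of follow-up.

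Section 8.2 restricts recorded events to those where, in the investigator's opinion, "they are directly associated with the collection of these samples". Appendix 1 identifies biopsy as the main risk to participants, lists complications up to and including death, and names no further safety process such as a data monitoring committee. Section 8.4 gives the chief investigator an ongoing review of risk and benefit.

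**The concern.** The two sections give opposite instructions for the same participant, and neither refers to the other. Because only sampling-related events are recorded, the adverse event log is the study's own record of the harm its sampling causes. A complication of sampling is one plausible reason for a participant to leave. If data collection then stops, the log shows that something happened but not how it ended.

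An event that was not serious at withdrawal could later lead to admission or death without the study team noting it. The duty in section 8.3 and Appendix 5 to report unexpected, related serious events to the ethics committee within 15 days runs from awareness, so it might never be triggered. The chief investigator's risk/benefit review would then rest on incomplete outcomes.

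**Working it through.** The protocol states no figure to reproduce, and no sample size, power or event count is involved. The check is a comparison of text with one worked timeline.

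| Situation | Section 6.7 | Section 8.3 |
|---|---|---|
| Event logged before withdrawal | Kept and used | Recorded |
| Follow-up of an event open at withdrawal | None | To recovery, death or 30 days after the last visit |
| Later worsening of an open event | Not collected | Would be seen during follow-up |
| Event first appearing after withdrawal | Not collected | Arguably outside the recording window, which closes at the last study visit |

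The second and third rows are the contradiction. The fourth row is a gap to which both sections contribute.

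**Timeline (illustrative).** Suppose a research biopsy is taken at the day 1 visit (Appendix 4). Bleeding is logged on day 3 while later visits are still due, and the participant withdraws that same day. Read the last visit as the last one attended, which is day 1.

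- Section 8.3: follow-up of an unresolved event may run to day 1 + 30 = day 31.
- Section 6.7: collection ends on day 3.
- Gap: 31 − 3 = 28 days in which one section requires follow-up and the other forbids it. Reading the last visit as a later scheduled one would only lengthen the gap.

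**What is kept and what is exposed.** The bleeding, and its seriousness as known on day 3, were obtained before withdrawal and are retained. The reporting duties in section 8.3 and Appendix 5 contain no exception for withdrawn participants. What is exposed is the resolution, any sequelae, a death, or an upgrade from non-serious to serious after day 3.

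**Can a site settle it alone?** Sections 12.4 and 12.5 have departures from the protocol logged and reported as breaches, and waivers are not approved. Whichever section a site follows, it departs from the other.

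**Reach.** The endpoint table in section 2.1 contains no safety outcome, and samples already taken are kept after withdrawal. The primary outcome and the feasibility proportion are therefore unaffected.

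**The case against.** Several points on the other side stand.

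- A reader might infer that 6.7 overrides 8.3. No text ranks one above the other, and a site could equally apply 8.3.
- A reader might infer that the participant vanishes from the safety record. That is wrong: what was logged before withdrawal is retained and stays reportable. Clinical care continues under the local service (section 12.10), and medical records remain the source (section 10.1).
- An event that first appears after withdrawal is arguably already outside the recording window in 8.3. Amending 6.7 alone would not capture it.
- Section 8.3 can leave an outcome unresolved at 30 days even when nobody withdraws.
- A complication need not lead to withdrawal. Further research samples are optional, and the week 6 and week 12 visits may be by telephone.
- Stopping collection at withdrawal is a recognisable way of respecting the participant's decision. The participant information sheet is not shown and may address safety follow-up. Even so, the protocol's own two sections would still disagree.

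A reader might also infer that serious complications are lost preferentially. For example, losing one of two events would take an observed rate from 2/75 = 2.7% to 1/75 = 1.3%. The documents do not support this. If harm prompts withdrawal, the event came first and is kept; if the event first appears after withdrawal, it did not prompt it. Only the later course of an open event, including an upgrade to serious, is exposed to loss that depends on harm.

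Nor does every withdrawal truncate safety follow-up. Assuming 5–15% withdraw gives 75 × 0.05 = 3.75 to 75 × 0.15 = 11.25, about 4 to 11 people, but the follow-up in 8.3 applies only to those with an adverse event.

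**Conclusion.** The point holds as an unreconciled contradiction of limited reach. For a participant who leaves with an unresolved sampling-related event, 6.7 and 8.3 cannot both be followed. Under a literal reading of 6.7, the outcome or worsening of that event is not captured. An event first appearing after withdrawal also goes unrecorded, for which 8.3 shares responsibility.

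The consequence is a less complete record of biopsy harm. The size cannot be derived, because the protocol gives neither a withdrawal rate nor a complication rate; the number affected is probably small. The conclusion rests on reading 6.7 as written, with no safety exception, and on the information sheet not resolving the matter. It is worth correcting because it concerns the main harm the study can cause and costs little to repair.

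**What to change.** Reconcile the two sections.

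- **Section 6.7:** limit the stop to samples and study outcome data. Possible wording: *After withdrawal no further samples and no further study outcome data (tumour response, survival) will be collected. Adverse events associated with samples already taken will continue to be recorded and followed up from medical records for the period in section 8.3, unless the participant objects.*
- **Section 8.3:** state the same for both the recording window and the follow-up. For a withdrawn participant, a sampling-related event first appearing after the last visit would then be recorded within the 30-day period. Changing only the follow-up sentence would leave that gap open.
- **Participant information sheet:** tell participants that this limited safety follow-up continues after withdrawal and that they may decline it.

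The cost is a sentence or two in each of the three places, a change to the consent wording, and review of medical records for a few withdrawn participants.

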#### 2.1. Table of endpoints/outcomes

Primary Objective:	Outcome Measure:	Timepoint
To characterise neoantigen profiles of oesophageal or gastroesophageal junction adenocarcinomas	Neoantigen profiles for individual patients with oesophageal or gastroesophageal junction adenocarcinomas	End of study

Secondary Objectives	Outcome Measures	Timepoint	
1- To determine the feasibility of neoantigen profiling using tumour biopsies of oesophageal or gastroesophageal junction adenocarcinomas	
 
Proportion of patients in which neoantigen profiles are successfully generated
 
	1- End of study	
2- To identify oesophageal or gastroesophageal junction adenocarcinoma neoantigens as candidate targets for immunotherapy	
 
Characterise pre-existing
 
T cell responses to
 
identified neoantigens
 
	2- End of study	
3- To investigate the relationship between neoantigen profiles and clinical outcomes	3- Correlate objective response rate, disease control rate, progression free survival and overall survival with neoantigen profiles.	3- End of study	
4- Recovery of RNA and DNA from samples	
 
Genomic and transcriptomic studies; neoantigen validation experiments.
 
	4- End of study	

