## 9.3.2. Secondary outcome analysis

The feasibility of neoantigen identification with the described approach in gastroesophageal adenocarcinoma patients, using routinely available clinical biopsy materials will be evaluated by assessing the proportion of patients in whom neoantigens are identified. The minimal amount of oesophageal adenocarcinoma tissue, and the qualitative and quantitative histological features associated with successful neoantigen identification will be evaluated to provide data on the features of optimal tumour specimens for future trials. Characterisation of pre-existing T cell responses to identified neoantigens will enhance evaluation of their potential utility as therapeutic targets for adoptive T cell and/or cancer vaccine approaches for the treatment of oesophageal adenocarcinoma. An exploratory analysis of the relationship between tumour neoantigen profiles and objective response rate, progression free and overall survival will be undertaken.

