## **10. DATA MANAGEMENT**

## 10.1. Data collection tools and source document identification

Medical records will be used as source data. The medical record will be flagged to state that the patient is participating in the PROTEAN study.

The PI or delegate will maintain source documents for each participant in the study, consisting of hospital medical records containing demographic and medical information.

An eCRF, using CASTOR Electronic Data Capture system, will be provided by TCTU. The study system will be based on the protocol for the study. Development and validation of the study database and quality control will be done according to TCTU procedures.

The eCRF will not collect more information than is required to meet the aims of the study and to ensure the eligibility and safety of the participant.

The PI may delegate eCRF completion but is responsible for completeness, plausibility and consistency of the eCRF. Delegated study staff will enter the data required by the protocol into the eCRFs following training in the definitions and methods used in completing the eCRF. Any queries will be resolved by the CI or delegated member of the study team. On completion of data collection, the PI must certify that the data entered into the eCRFs is complete and accurate. PI sign-off of the eCRF will be embedded in the eCRF with the PI using their own login.

Data verification, cleaning and extraction of data will be performed as per TCTU local procedures and detailed in the Data Management Plan.

Data preservation and sharing will be in accordance with established procedures at the University of Dundee. All electronic data will be stored on secure University of Dundee or cloud-based servers which have restricted access and have disaster recovery systems in place.

General laboratory data methods and results will be documented in laboratory notebooks and then analysed and written up for publication for dissemination to the scientific community. All electronic data will be stored on password-protected computers in secure staff access - controlled offices at investigator sites. All data and laboratory notebooks will be retained for at least ten years, in accordance with general RCUK guidelines.

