### 12.10. Post study care

Participants will be treated and followed up as per the local cancer service.

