#### Justification:

The main risk for participants is from the biopsy of tumour tissue. Where possible this will be done at the same time as standard care biopsy or tumour resection.

What are the key risks related to assessments you plan to undertake in this study?			
Intervention	Hazard	How will these risks be minimised?	
Blood samples	Discomforts of drawing blood include temporary discomfort from the needle stick, the possibility of pain or bruising at the site of the blood draw, occasional feelings of light headedness and, rarely, infection at the site of the blood draw	Blood samples will be taken at the same time as blood draw for routine care purposes whenever possible. Staff taking blood will be experienced in venepuncture.	
Biopsy	Risk of serious complications, such as bleeding, pneumothorax, infection, or even death, depending on the site of disease. Risks vary according to the technical aspects of the biopsy (e.g. size of needle and location or size of the required specimen), the experience or training of the medical professional performing the biopsy, and participant characteristics. The risks for both major complications and AEs increase with multiple biopsies.	Previously collected samples will be used when available, or samples will be taken at the same time as clinically indicated procedures whenever possible. In other instances, the biopsies will be only performed if the risk to the participant is low or moderate. Only samples at baseline are required as per protocol, other samples will only be collected as far as possible during standard care procedures. In considering the study design we have reflected upon the key ethical guidance on research biopsies in cancer research provided in the American Society of Clinical Oncology Research Statement: Ethical Framework for Including Research Biopsies in Oncology Clinical Trials. Journal of Clinical Oncology 37, no. 26 (September 10,	

	2019)2368-2377. Our approach in this study is consistent with this guidance and accordingly is consistent with the practice of oncology studies of this type in a global context.
Outline any other processes that have been put in place (e.g. DMC, independent data review, etc.) Nil	to mitigate risks to participant safety

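### Section 6.7 has one level of withdrawal, so leaving the study or being withdrawn by the investigator also ends collection of outcomes that remain in routine records

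*Protocol*

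**What the plan says.** Section 6.7 lets participants leave at any time. It also gives the investigator a route: "The investigator may withdraw a participant at any time if it is in the best interest of the participant", with the added condition that staying in would harm the participant. One consequence covers both routes. "If a participant withdraws or is withdrawn from the study, the research team will retain any data and samples obtained" up to that point, and then "No further data or samples will be collected after withdrawal". No intermediate status is defined.

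Secondary objective 3 (section 2.1) is to "Correlate objective response rate, disease control rate, progression free survival and overall survival with neoantigen profiles". Section 6.4 lists RECIST status and overall survival as the outcome assessments. Section 9.3.2 sets the standing of the analysis: "An exploratory analysis of the relationship between tumour neoantigen profiles and objective response rate, progression free and overall survival will be undertaken". The study summary gives 18 weeks of follow-up, and section 6.5 plans none beyond that.

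On where outcomes come from, section 10.1 states "Medical records will be used as source data". Section 7 says that there is no treatment intervention and that standard care continues. Section 12.10 adds: "Participants will be treated and followed up as per the local cancer service".

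On sampling, Appendix 1 states "Only samples at baseline are required as per protocol". The study flow chart and section 6.4 make later biopsies and additional research bloods optional, and Appendix 4 allows visits 3 and 4 by telephone.

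**The concern.** In a study without treatment, the burden on a participant comes from sampling and contacts. Withdrawing someone for their well-being therefore needs to stop those and nothing more. Reading the hospital record adds no burden, yet section 6.7 stops that too.

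Withdrawal because a participant is unwell may well come shortly before progression or death. If it does, censoring at withdrawal is informative: the participant's neoantigen profile stays in the analysis, but the event does not. The cohort is 75 participants followed for 18 weeks, so events are few. Section 9.5 deals only with failed samples, and no analysis plan can recover outcomes that the protocol forbids sites to collect.

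**Working it through.** The protocol gives no withdrawal rate, event count or formal sample size, so there is no stated figure to reproduce. What follows is illustrative.

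**Inputs from the protocol.** 75 participants (section 9.2); 18 weeks of follow-up (study summary); most patients die within a year of diagnosis (section 1.1).

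**Assumptions not in the protocol.** Exponential survival from enrolment with a median of 9 or 12 months; 10% to 50% of those who would die by week 18 are withdrawn first and censored between half of their survival time and death; a binary profile split 50:50; a true hazard ratio (HR) of 1.0 or 0.5.

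**Step 1: expected deaths by week 18.** 18 weeks = 126 days = 0.345 years = 4.14 months.
- Median 12 months: survival = 2^(−0.345) = 0.787; deaths = 75 × 0.213 = 16.0.
- Median 9 months: survival = 2^(−4.14/9) = 0.727; deaths = 75 × 0.273 = 20.5.

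**Step 2: effect on survival.** Kaplan-Meier estimates from a simulation of 200,000 patients, loss unrelated to profile, HR 1.0. Deaths lost = expected deaths × share lost.

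| Median | Early deaths lost | Deaths lost of 75 participants | True week-18 survival | Observed |
|---|---|---|---|---|
| 9 months | 10% | 2.1 | 0.73 | 0.75 |
| 9 months | 25% | 5.1 | 0.73 | 0.79 |
| 9 months | 50% | 10.3 | 0.73 | 0.85 |
| 12 months | 10% | 1.6 | 0.79 | 0.81 |
| 12 months | 25% | 4.0 | 0.79 | 0.83 |
| 12 months | 50% | 8.0 | 0.79 | 0.89 |

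A hand check of the 12-month, 25% row: suppose 7 of 75 (about 10%) are withdrawn and 60% of them would have died by week 18. Deaths lost = 7 × 0.60 = 4.2, leaving 11.8. With roughly 70 at risk, 1 − 11.8/70 = 0.83. If withdrawal were unrelated to prognosis, only 7 × 0.213 = 1.5 deaths would be lost and survival would not be biased.

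**Step 3: effect on the profile-outcome association.** Let q0 and q1 be the shares of early deaths lost in the reference and comparison profile groups. Approximately, observed HR = true HR × (1 − q1)/(1 − q0).

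| q0, q1 | True HR | Approximation | Simulated (9 and 12 months) |
|---|---|---|---|
| equal, 10% to 50% | 1.0 | 1.0 | 0.98 to 1.03 |
| equal, 10% to 50% | 0.5 | 0.5 | 0.49 to 0.50 |
| 50%, 25% | 1.0 | 1.5 | 1.45 and 1.48 |
| 50%, 25% | 0.5 | 0.75 | 0.74 and 0.75 |
| 50%, 0% | 1.0 | 2.0 | 1.95 and 1.99 |
| 50%, 0% | 0.5 | 1.0 | 0.97 and 0.99 |

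With equal loss the HR is essentially unchanged. With unequal loss it moves, and the direction depends on which group loses more.

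**Step 4: what equal loss costs.** With a 50:50 split, the standard error of log HR is about 2/√(deaths). At 16 deaths it is 0.50, so the 95% limits lie a factor exp(1.96 × 0.50) = 2.7 either side of the estimate. At 12 deaths it is 0.58, a factor of 3.1.

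**The case against.** A reader might infer that anyone who refuses further biopsies or bloods loses their follow-up. The documents do not support that. Later biopsies and additional bloods are optional, visits 3 and 4 may be by telephone, and visits outside their windows are not breaches. A participant can stop sampling and stay in; section 6.7 applies only to someone who leaves or is taken out of the study.

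A reader might also infer that objective 3 is biased as things stand. That is not shown either. The objective is an association, and step 3 shows that it barely moves when loss is unrelated to profile. Nothing in the protocol indicates that loss would differ by profile, and section 7 says that care is not affected by the data generated.

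Further points on that side have weight. The investigator route requires that continuing would be detrimental; once the baseline biopsy is done little remains to be detrimental, so the route may seldom be used. Section 6.7 does not name deterioration. The withdrawal and loss rates above are assumptions. The survival statement in section 1.1 runs from diagnosis, whereas the cohort mixes people before, between and after treatments. The analysis is exploratory. Stopping all data at withdrawal is a defensible, cautious consent choice, and the consent wording was not available to check.

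These points limit the size of the problem but do not remove it. The bar on later data is explicit and covers both routes. The harm test in section 6.7 is met by stopping procedures, so it gives no reason to stop reading the record.

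**Conclusion.** The point holds in a limited form. Section 6.7 causes avoidable loss of response, progression and survival data for participants who leave or are withdrawn by the investigator, although the records remain available.

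If withdrawals cluster before death, survival is overstated: by about 2 percentage points with 10% of early deaths lost, 5 to 6 with a quarter lost, and 10 to 12 with half lost, under the assumed 9- to 12-month medians. The same mechanism applies to progression-free survival; it was not quantified. The profile-outcome association can be biased if loss differs by profile; otherwise it mainly loses precision, and with about 16 to 21 deaths it is imprecise even with complete data.

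The primary outcome and the feasibility outcome are unaffected once the baseline biopsy is in hand, because data and samples up to withdrawal are kept. This is a cheap improvement to an exploratory secondary analysis, not a threat to the study's main purpose.

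**What to change.** Replace the last sentence of section 6.7 with two levels:

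- (a) Stop study procedures and contacts. Response, progression, treatment and survival are still collected from routine records to week 18.
- (b) Stop all further data collection, at the participant's explicit request.

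Treat investigator withdrawal on well-being grounds as level (a) unless the participant asks for (b). Record the level, the date and the reason (if given) in the eCRF. Add a sentence that declining optional samples is not withdrawal. Align the participant information sheet and consent form, and settle how the change applies to people who have already consented.

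The cost is one amendment (a paragraph in section 6.7, a consent line and a small eCRF entry) and continued note abstraction for a few participants. The right to stop everything is kept.
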